6.4.3 Supine BP and pulse

The supine BP and pulse must be measured prior to the standing BP and pulse. After the patient rests in the supine position for at least 5 minutes, supine BP and pulse will be determined from three replicate measurements obtained at least 1 minute apart. All three readings must be recorded. For study analyses, the average of the three BP and pulse readings will be used.

6.4.4 Standing BP and pulse

After the supine BP and pulse measurements are obtained, the patient will stand for 2 to 3 minutes. After this time, the BP will be measured with the arm supported at the level of the heart. Standing BP and pulse will be determined from three replicate measurements obtained at least 1 minute apart. All 3 readings must be recorded. For study analyses, the average of the three BP and pulse readings will be used.

If a new occurrence of previously absent orthostatic hypotension is demonstrated, it should be recorded as AE. The investigator may consider reducing concomitant anti- hypertensive medication to alleviate signs and symptoms of orthostatic hypotension.

6.4.5 Weight

The patient's weight will be recorded in kilogram (kg) to one decimal place, with light clothing and no shoes. All readings should be recorded as accurately as possible and the same calibrated scale should be used for all assessments for a given patient. Body weight assessments should preferably be conducted in the morning after an overnight fast and after emptying the bladder.

6.5 Six Minute Walk Test

The 6MWT is a practical simple test that requires a 100-ft hallway but no exercise equipment or advanced training for technicians. Walking is an activity performed daily by all but the most severely impaired patients. This test measures the distance that a patient can quickly walk on a flat, hard surface in a period of 6 minutes (the 6MWD). It evaluates the global and integrated responses of all the systems involved during exercise, including the pulmonary and cardiovascular systems, systemic circulation, peripheral circulation, blood, neuromuscular units, and muscle metabolism. It does not provide specific information on the function of each of the different organs and systems involved in exercise or the mechanism of exercise limitation, as is possible with maximal cardiopulmonary

exercise testing. The self-paced 6MWT assesses the submaximal level of functional capacity. Most patients do not achieve maximal exercise capacity during the 6MWT; instead, they choose their own intensity of exercise and are allowed to stop and rest during the test. However, because most activities of daily living are performed at submaximal levels of exertion, the 6MWD may better reflect the functional exercise level for daily physical activities.¹⁷

6.6 Collection of Kansas City Cardiomyopathy Questionnaire (KCCQ)

The KCCQ (see appendix B) is a disease-specific health status instrument composed of 23 items that quantify the domains of physical limitation, symptoms, self-efficacy, social limitation, and quality of life limitation from heart failure. The overall summary score and all domains have been independently demonstrated to be valid, reliable, and responsive to clinical change. Scores range from 0 to 100. For the KCCQ overall summary score, a small but clinically meaningful change is considered to be ≥ 5 points.¹⁸ The patients will fill in PRO (KCCQ) paper form under the supervision of the site staff.

6.7 Laboratory assessments

Blood and urine samples for determination of clinical chemistry, hematology, urinalysis and biomarker testing will be taken at the times indicated in the Study Plan (see Table 1). Any additional laboratory safety samples taken at the investigator's discretion will be analyzed locally.

It is recommended that patients do not have their baseline diuretics changed based upon natriuretic peptide levels, and that the patient's primary cardiologist be blinded to the BNP and NTproBNP data collected throughout the trial. There have been varying results with trials of NTproBNP guided clinical management of heart failure. Two randomized clinical trials have shown no clear benefit.²⁴⁻²⁵ Given the uncertainty of benefit, neither serial collection nor treatment based upon NTproBNP levels are currently endorsed by ACC/AHA guidelines.²⁶ For these reasons, it is recommended that heart failure medication changes not be made based on natriuretic peptide levels. If a patient is clinically symptomatic or endorses signs or symptoms of volume overload, clinical judgment should be used and diuretic adjustments made as warranted.

7 BIOLOGICAL SAMPLING PROCEDURES

7.1 Volume of blood

The total volume of blood that will be drawn from each patient for this study is listed in Table 4 below. The collection of additional samples is performed locally at the discretion of the investigator and recorded in the eCRF as appropriate, thus requiring additional sample volumes.

Table 4 Volume of blood to be drawn from each patient

Assessment	Sample volume (mL)	Number of Samples	Total Volume (mL)
HbA1c	4 mL whole blood	4	16 mL
Glucose	2 mL whole blood	3	6 mL
BNP	2 mL whole blood	4	8 mL
NTproBNP	2 mL whole blood	4	8 mL
CBC	4 mL whole blood	3	12 mL

Renal Panel/Uric Acid	4 mL whole blood	5	20 mL
Serum, plasma, buffy coat, biobanking	40 mL whole blood	2	80 mL
Total			150 mL

7.2 Handling, storage and destruction of biological samples

Blood and urine samples will be processed by local staff for shipment to the central laboratory (Quest Diagnostics). All samples should be taken by adequately trained study personnel and handled in accordance with instructions in the central laboratory manual. Up to date reference ranges will be provided during the study and laboratory results will be compared to the laboratory standard normal ranges and flagged if they are outside the normal range. The Investigator should make an assessment of any clinically significant abnormalities in the laboratory reports. The laboratory reports should be signed, dated and retained at the study site as source data for laboratory variables.

The clinical chemistry, hematology, and urinalysis samples will be disposed after analyses.

8 SAFETY

8.1 Definition of adverse events (AE)

An AE is the development of an undesirable medical condition or the deterioration of a pre-existing medical condition following or during exposure to a pharmaceutical product, whether or not considered causally related to the product. An undesirable medical condition can be symptoms (eg, nausea, chest pain), signs (e.g., tachycardia, enlarged liver) or the abnormal results of an investigation (e.g., laboratory findings, electrocardiogram). In clinical studies, an AE can include an undesirable medical condition occurring at any time, including run-in or washout periods, even if no study treatment has been administered. The term AE is used to include both serious and non-serious AEs.

8.2 Definitions of serious adverse event (SAE)

An SAE is an AE occurring during any study phase (i.e., run-in, treatment, follow-up), that fulfills one or more of the following criteria:

- Results in death
- Is immediately life-threatening
- Requires in-patient hospitalization or prolongation of existing hospitalization
- Results in persistent or significant disability or incapacity
- Is a congenital abnormality or birth defect
- Is an important medical event that may jeopardize the patient or may require medical intervention to prevent one of the outcomes listed above.

Any event of cancer, drug dependency/abuse, laboratory abnormalities fulfilling the Hy's law definition or overdose (defined as the accidental or intentional ingestion of any dose of the

investigational product that is considered both excessive and medically important) should be reported as an SAE using the most relevant SAE criteria, as judged by the Investigator.

8.2.1 Classification of Death

Deaths will be sub-classified by CV and non-CV primary cause. CV death includes sudden cardiac death, death due to acute MI, death due to heart failure, death due to a cerebrovascular event, death due to other CV causes (e.g., pulmonary embolism, aortic disease, CV intervention), and deaths for which there was no clearly documented non-CV cause (presumed CV death).

Additionally, deaths will be sub-classified by coronary heart diseases death (CHD death) and non-CHD death. CHD death includes Sudden Cardiac Death, Death due to Acute MI, and the subset of Death due to other CV Causes that are secondary to a coronary revascularization procedure.

8.2.2 Universal classification of Myocardial Infarction (MI)

The Third Universal MI definition¹⁹ will be used as study specific MI criteria.

8.2.3 Definition of Stroke

Stroke is defined as an acute episode of neurologic dysfunction attributed to a central nervous system vascular cause. Stroke should be documented by imaging (eg, CT scan or magnetic resonance imaging [MRI] scan). Evidence obtained from autopsy can also confirm the diagnosis. Stroke will be sub classified, when possible, as either:

8.2.4 Primary ischemic stroke

Primary ischemic stroke is defined as an acute episode of focal brain, spinal, or retinal dysfunction caused by an infarction of central nervous system tissue and documented by imaging. A primary ischemic stroke may also undergo hemorrhagic transformation (i.e., no evidence of hemorrhage on an initial imaging study, but appearance on a subsequent scan).

8.2.5 Primary hemorrhagic stroke

Primary hemorrhagic stroke is defined as an acute episode of focal or global brain, spinal, or retinal dysfunction caused by non-traumatic intraparenchymal, intraventricular, or subarachnoid hemorrhage as documented by neuroimaging or autopsy. Microhemorrhages (<10 mm) evident only on MRI are not considered to be a hemorrhagic stroke. Subdural and epidural bleeding will be considered intracranial hemorrhage, but not strokes.

8.2.6 Unclassified stroke

Stroke with unknown etiology will be classified as unclassified stroke if the type of stroke could not be determined by imaging or other means.

8.2.7 Hospitalizations for heart failure

In the event that a patient is hospitalized for heart failure over the course of the study, source documents will be obtained to adjudicate events. See appendix A for detailed information.

8.2.8 Acute Kidney Injury

Acute kidney injury is defined as a doubling of creatinine, consistent with the modified RIFLE criteria for stage 2 acute kidney injury.

8.2.9 Ketoacidosis (DKA)

Be aware that postmarketing cases show a possible association between sodium-glucose cotransporter-2 (SGLT2) inhibitor use and the development of a high anion gap metabolic acidosis accompanied by elevation in urine or serum ketones, frequently in the setting of only mildly elevated glucose levels (euglycemic DKA). Investigators are strongly encouraged to

instruct patients and caregivers about the signs and symptoms of ketoacidosis, such as tachypnea or hyperventilation, anorexia, abdominal pain, nausea, vomiting, lethargy, or mental status changes; evaluate for the presence of ketoacidosis in patients experiencing such signs or symptoms – using provided urine ketone testing kits; discontinue study medication and advise patients to go to the nearest emergency department if ketoacidosis is confirmed; and take appropriate measures to correct the ketoacidosis and to monitor glucose levels. Investigators are also strongly encouraged to avoid concomitant risk factors potentially predisposing to DKA, including carbohydrate-restricted diets and marked reductions in insulin dose (in patients with established type 2 diabetes) during the study among patients receiving insulin at baseline (above and beyond reductions in insulin dose (for patients with established type 2 diabetes) specified in the study protocol). Advise patients to alert you and seek medical attention immediately if they experience symptoms consistent with DKA such as: nausea, vomiting, abdominal pain, confusion, change in breathing pattern and unusual fatigue or sleepiness.

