The U.S. Food and Drug Administration (FDA) recently reported a warning for sodium-glucose cotransporter-2 (SGLT2) inhibitors which may lead to ketoacidosis, a serious condition where the body produces high levels of blood acids called ketones that may require hospitalization. At the time of this report there were 20 cases of acidosis reported as diabetic ketoacidosis (DKA), ketoacidosis, or ketosis in patients treated with SGLT2 inhibitors. DKA, a subset of ketoacidosis or ketosis in diabetic patients, is a type of acidosis that usually develops when insulin levels are too low or during prolonged fasting. DKA most commonly occurs in patients with type 1 diabetes and is usually accompanied by high blood sugar levels. The FDA reported cases were not typical for DKA because most of the patients had type 2 diabetes and their blood sugar levels, when reported, were only slightly increased compared to typical cases of DKA. Factors identified in some reports as having potentially triggered the ketoacidosis included major illness, reduced food and fluid intake, and reduced insulin dose. Although the risk of euglycemic DKA is estimated to be very low in this study (given the short duration of treatment, and the fact that patients with type 2 diabetes are at lower risk for DKA than type 1 diabetes, and patient without diabetes are likely not at risk for DKA) all patients will be provided with home urine ketone testing kits, and patients will be monitored for symptoms of DKA during in-person visits and study-related phone calls. Patients will be instructed to

self-test for urine ketones and be directed to the closest emergency department if the urine ketone test is more than mildly positive. The instances of DKA (if any) will be closely monitored as SAE of special interest by the study investigators, as well as the Independent Data and Safety Monitoring Committee. In addition, all patients in this study will continue taking glucose-lowering medications (other than open-label SGLT-2 inhibitors) as background therapy. These drugs are widely used anti-hyperglycemic treatments and will be prescribed according to the approved label in patients with known diabetes.

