1.3.3 Protection against Risks

This study has been designed with appropriate measures in place so as to monitor and minimize any of the potential health risks to participating patients. This includes careful monitoring of patients'

vital signs and laboratory values, and the temporary and if necessary permanent discontinuation of investigational product in individual patients in whom a potential health risk or a laboratory abnormality of clinical concern has been identified. Further, in order to ensure the safety of all patients participating in this study, an Independent Data and Safety Monitoring Committee (IDSMC) will be formed that will continuously review safety data, including the incidence of serious adverse events (SAEs), and conduct assessments to ensure the ongoing safety of study patients. The IDSMC responsibilities, authorities, and procedures are documented in an IDSMC charter. The personnel involved in the clinical study at will remain blinded to these analyses and will have no knowledge of the results presented to the IDSMC.

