4.2 Exclusion criteria

1. Decompensated heart failure (hospitalization for heart failure within 7 days prior to screening)
2. History of type 1 diabetes
3. History of diabetic ketoacidosis
4. Estimated glomerular filtration rate (eGFR) < 20 at the screening visit by modified MDRD equation $\text{GFR} (\text{mL/min}/1.73\text{ m}^2) = 175 \times (\text{Scr})^{-1.154} \times (\text{Age})^{-0.203} \times (0.742 \text{ if female}) \times (1.210 \text{ if African American})$
5. Admission for an acute coronary syndrome (ST-elevation MI, non-ST-elevation MI, or unstable angina), percutaneous coronary intervention, or cardiac surgery within 30 days prior to the screening visit.
6. Admission for cardiac resynchronization therapy (CRT) within 90 days prior to the screening visit.
7. Planned cardiovascular revascularization (percutaneous intervention or surgical) or major cardiac surgery (coronary artery bypass grafting, valve replacement, ventricular assist device, cardiac transplantation, or any other surgery requiring thoracotomy, or transcatheter aortic valve replacement) or CRT within the 90 days after the screening visit.
8. Participation in any interventional clinical trial (with an investigational drug or device) that is not an observational registry within 15 days of the screening visit.
9. History of hypersensitivity to dapagliflozin
10. For women of child-bearing potential: Current or planned pregnancy or currently lactating.

Women of childbearing potential are defined as any female who has experienced menarche and who is NOT permanently sterile or postmenopausal. Post menopausal is defined as 12 consecutive months with no menses without an alternative medical cause. Women of child-bearing potential, who are sexually active, must agree to use a medically-accepted method of birth control for the duration of the study. Acceptable birth control methods include: (1) surgical sterilization (such as a hysterectomy or bilateral tubal ligation), (2) progesterone hormonal contraceptives (birth control pills or implants), (3) barrier methods (such as a condom or diaphragm) used with a spermicide, or (4) an intrauterine device (IUD). Women of child-bearing potential will have a urine pregnancy test at every clinic visit and it must be negative to continue study participation.

11. Life expectancy < 1 year at the screening visit

12. Patients who are volume depleted based upon physical examination at the time of the screening or randomization visit

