5.9.1 General discontinuation criteria

1. Patient decision. The patient is at any time free to discontinue treatment, without prejudice to further treatment.
2. Adverse Events, i.e., any clinical AE, laboratory abnormality or concurrent illness which, in the opinion of the investigator, indicates that continued participation in the study is not in the best interest of the patient.
3. Severe non-compliance to protocol as judged by the investigator and/or
4. Risk to patients as judged by the investigator.
5. Incorrectly enrolled patients.
6. Patient lost to follow-up.

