5.9.2 Study-specific discontinuation criteria

1. Doubling of serum creatinine above the baseline value confirmed by a repeated measurement within one week.
2. Recurrent severe hypoglycemic events, defined as ≥ 2 severe events (a severe hypoglycemic event is defined as symptomatic events requiring external assistance due to severe impairment in consciousness or behavior with a capillary or plasma glucose value <54 mg/dL or blood glucose <54 mg/dL). This definition should be applied after possible contributing factors (eg, excessive physical activity, dietary and medication factors) have been excluded or addressed by the investigator.
3. Pregnancy confirmed by a positive pregnancy test or otherwise verified.

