5.9.7 Restart of study medication

Whenever possible, and at every study visit, restart of randomized study medication should be encouraged, even if a PTDV was previously completed.

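### The protocol does not make a study-drug stop for confirmed ketoacidosis permanent, and its restart rule makes no exception for it

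*Protocol*

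**What the plan says.** **The stop.** Protocol 8.2.9 asks sites to "discontinue study medication and advise patients to go to the nearest emergency department if ketoacidosis is confirmed". The sentence opens "Investigators are strongly encouraged to", so it is advice, and it does not say how long the stop lasts.

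**The listed stopping criteria.** Section 5.9.2 has three: confirmed creatinine doubling ("Doubling of serum creatinine above the baseline value confirmed by a repeated measurement within one week"), recurrent severe hypoglycemia, and pregnancy. Ketoacidosis is not among them. Section 5.9.1 adds general criteria, including adverse events on the investigator's opinion and "Risk to patients as judged by the investigator".

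**The restart rule.** Section 5.9.7 says: "Whenever possible, and at every study visit, restart of randomized study medication should be encouraged, even if a PTDV was previously completed". The PTDV is the premature treatment discontinuation visit.

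**Entry.** Exclusion criterion 3 in section 4.2 is "History of diabetic ketoacidosis".

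**General safeguards.** Section 1.3.3 lists among its protections "the temporary and if necessary permanent discontinuation of investigational product in individual patients in whom a potential health risk" has been identified. Section 1.3.2 says that any DKA cases "will be closely monitored as SAE of special interest by the study investigators" and by the independent safety committee (IDSMC).

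**The concern.** A site managing a patient who has recovered from ketoacidosis will look for a rule on whether study drug may be resumed. The only one it will find is 5.9.7, which favors restart at each visit and does not ask why drug was stopped. Yet the protocol regards a past DKA episode as sufficient reason not to start the drug, and 8.2.9 has just asked for it to be stopped. At stake is renewed exposure of a patient who has had a serious event that 8.2.9 links to this drug class. The issue is patient protection, not the validity of the efficacy comparison.

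**Working it through.** No figure in the plan depends on this point, so the check is a comparison of texts. The question is whether any of them makes a ketoacidosis stop permanent or removes it from the restart rule.

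| Protocol or SAP text | On stopping | On restart after ketoacidosis |
|---|---|---|
| 8.2.9 | Encourages a stop once confirmed | Silent |
| 6.3.1 | Sends confirmed cases to the emergency department; study drug not mentioned | Silent |
| 5.9 lead-in | Uses *should*; does not say permanently | Silent |
| 5.9.1 | Investigator opinion on adverse events and risk | Allows drug to be withheld; does not require it |
| 5.9.2 | Three criteria, none of them ketoacidosis | Silent |
| 5.9.3 | Procedures for permanent discontinuation, without saying which events trigger it | Silent |
| 5.9.7 | Not applicable | Encourages restart, even after a PTDV; no exception |
| 1.3.3 | Foresees temporary and permanent stops in general terms | Does not say which events need which |
| SAP 10.2, item 3.0 | Dosing continued after an adverse event judged to contraindicate it is an important deviation, reviewed case by case | An analysis rule that depends on investigator opinion; no bar |

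Three steps follow.

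1. A PTDV does not settle the matter. One might take it as the mark of a final stop, but 5.9.7 expressly reaches past it.
2. Entry and on-study handling differ. If a patient with prior DKA is randomized by mistake, section 5.4 requires immediate contact with the study team physician and a documented rationale if drug continues. No equivalent step is required before restarting a patient whose DKA occurred on study.
3. A site that restarted drug after ketoacidosis would therefore not be breaking a stated rule, unless the investigator had judged further dosing contraindicated.

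**Who is concerned.** Section 1.3.2 says that patients without diabetes are likely not at risk, so the relevant group is mainly dapagliflozin patients with diabetes. Section 12.2 plans about 128 patients with diabetes, and half of the study population receives placebo (1.3.4): 128 / 2 = 64. At the cap of about 146 in section 4, 146 / 2 = 73. These are denominators only. The documents give no DKA rate, so no expected number of cases can be derived.

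**The case against.** The strongest reply is that re-dosing would have to pass several checks. The patient has been sent to an emergency department. SAEs must be reported by the end of the next business day (8.4). The IDSMC can see treatment codes (5.11.4). Under 5.9.1 the investigator can judge at any later visit that drug poses a risk, and *whenever possible* in 5.9.7 leaves room for that. SAP 10.2 item 3.0 treats dosing after a contraindicating event as a deviation. The protocol also speaks of temporary interruption when it means one, as for volume depletion in 1.3.2, which suggests that *discontinue* in 8.2.9 was meant to last. Nor does the advisory tone of 8.2.9 carry much weight, since the 5.9 lead-in also says *should*.

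All of this stands as a reason to think re-dosing unlikely. None of it prohibits re-dosing: reporting follows the event, no approval is required before restart, and discretion allows drug to be withheld without requiring it.

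A reader might also infer more than the documents support:

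- **That every 5.9.2 stop needs a permanent bar.** Pregnancy is already closed: 13.3 stops the product and exclusion criterion 10 requires a negative test to continue. Whether to resume after creatinine recovers, or after recurrent hypoglycemia has been dealt with, is a legitimate judgment call. The argument from exclusion criterion 3 does not extend to either.
- **That leftover tablets make restart easy.** All 105 are dispensed at randomization (5.6.3), but a patient who discontinues returns all study medication (5.9.3), and the PTDV includes drug return and logging the discontinuation in the IVR/IWR system (6.2.6). Restart after the PTDV would need a deliberate redispensing.
- **That re-exposure is capped at half the course.** Restart at week 6 would leave 84 − 42 = 42 of 84 days. But 5.9.7 says every visit, and the week 4 phone contact is a visit, which would leave 84 − 28 = 56. Neither figure is an established exposure.

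**Conclusion.** The point holds for ketoacidosis alone, as a low-cost improvement of minor severity. The stop in 8.2.9 is not stated to be permanent, the event is missing from 5.9.2, and the restart rule in 5.9.7 makes no exception for it. The existing controls make re-dosing unlikely without ruling it out.

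The size is a rare but serious event in very few patients. That rests on the protocol's own description of the risk as very low in 1.3.2, because no rate is given. It also assumes that no document outside the protocol and SAP, such as the IDSMC charter, already bars restart. No effect on bias, power or type I error follows.

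**What to change.** Two additions by amendment:

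1. In 5.9.2, a fourth criterion: *Confirmed ketoacidosis (permanent stop).*
2. In 5.9.7, one sentence: *Study medication must not be restarted after confirmed ketoacidosis.* Patients stopped for this reason stay in follow-up under 5.9.4.

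The other 5.9.2 criteria can stay as they are. No new test or visit is needed. The cost is slightly less drug exposure in very few patients. For patients who continue visits under 5.9.4, the KCCQ is still collected at the PTDV (6.2.6) and at week 12 (6.2.4), so the change need not cost primary endpoint data.
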